## 6. STUDY VACCINE AND ADMINISTRATION

### 6.1. Description of study vaccine

The candidate vaccine to be used has been developed and manufactured by GSK Biologicals.

The Quality Control Standards and Requirements for the candidate vaccine are described in separate Quality Assurance documents (e.g. release protocols, certificate of analysis) and the required approvals have been obtained.

The vaccines are labelled and packed according to applicable regulatory requirements.

**Table 10 Study vaccine**

Vaccine name	Formulation	Presentation	Volume to be administered	Number of doses
Encepur Adults	TBE, K23 strain=1.5µg; Al(OH) 3	Whitish, turbid suspension for injection in a pre-filled syringe	0.5 mL	1

### 6.2. Storage and handling of study vaccine

The study vaccine must be stored at the respective label storage temperature conditions in a safe and locked place. Access to the storage space should be limited to authorized study personnel. The storage conditions will be assessed during pre-study activities under the responsibility of the sponsor study contact. The storage temperature should be continuously monitored with calibrated (if not validated) temperature monitoring device(s) and recorded. Refer to the Module on Clinical Trial Supplies in the SPM for more details on storage of the study vaccine.

Temperature excursions must be reported in degree Celsius.

Any temperature excursion outside the range of +2.0 to +8.0°C (for +2 to +8°C/+36 to +46°F label storage condition) impacting investigational medicinal products (IMPs) must be reported in the appropriate (electronic) temperature excursion decision form (Advanced Temperature Excursion Analysis and Management [ATEAM]). The impacted IMPs must not be used and must be stored in quarantine at label temperature conditions until usage approval has been obtained from the sponsor.

Refer to the Module on Clinical Trial Supplies in the SPM for details and instructions on the temperature excursion reporting and usage decision process, packaging and accountability of the study vaccine.

### 6.3. Dosage and administration of study vaccine

**Table 11 Dosage and administration**

Type of contact and timepoint	Study group	Treatment name	Volume to be administered	Route 	Site	
					Location	Laterality 
Visit 23.1	all study groups 	Encepur Adults	0.5 ml	IM	Deltoid	Non-dominant
Visit 24.1	all study groups 	Encepur Adults	0.5 ml	IM	Deltoid	Non-dominant
Visit 25.1	all study groups 	Encepur Adults	0.5 ml	IM	Deltoid	Non-dominant
Visit 26.1	all study groups 	Encepur Adults	0.5 ml	IM	Deltoid	Non-dominant
Visit 27.1	all study groups 	Encepur Adults	0.5 ml	IM	Deltoid	Non-dominant

Intramuscular (IM)

The non-dominant arm is the preferred arm of injection. In case it is not possible to administer the vaccine in the non-dominant arm, an injection in the dominant arm may be performed.

Only subjects with an NT antibody titre below 10 at a scheduled visit will receive 6 months later at an unscheduled visit a second booster vaccination.

### 6.4. Replacement of unusable vaccine doses

In addition to the vaccine doses provided for the planned number of subjects (including over-randomisation when applicable), at least 50% additional vaccine doses will be supplied to replace those that are unusable.

### 6.5. Contraindications to subsequent vaccination

The following events constitute absolute contraindications to administration of *Encepur Adults*. If any of these events occur during the study, the subject must not receive a dose of vaccine but may continue other study procedures at the discretion of the investigator.

- Anaphylaxis following any previous administration of vaccine.
- Pregnancy (see Section 8.2.1).
- Any condition that in the judgment of the investigator would make intramuscular injection unsafe.

The following events constitute contraindications to administration of *Encepur Adults* at that point in time; if any of these events occur at the time scheduled for vaccination, the subject may be vaccinated at a later date, within the time window specified in the protocol, or withdrawn at the discretion of the investigator.

- Acute disease on the day of booster vaccination (acute disease means moderate or severe illness with or without fever). The vaccine may be administered to subjects with minor illness such as mild diarrhoea or mild upper respiratory tract infection with oral temperature <38.0°C).

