**5.6.12. Physical examination**

Perform a physical examination of the subject, including assessment of oral body temperature and resting vital signs: systolic/diastolic blood pressure and heart rate at visits specified in [Table 5](#). Collected information needs to be recorded in the eCRF.

If the investigator determines that the subject's health on the day of vaccination temporarily precludes vaccination, the visit will be rescheduled.

Treatment of any abnormality observed during physical examination has to be performed according to local medical practice outside this study or by referral to an appropriate health care provider.

The weight of the subject will be measured and the information will be recorded in the eCRF at each vaccination visit.

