### **9.2.2. Subject withdrawal from study vaccine**

Not applicable.

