## **10.5. Derived and transformed data**

- Immunogenicity

- The cut-off value is defined by the laboratory before the analysis and is described in Section 5.7.3.
- A seronegative subject is a subject whose titre is below the cut-off value.
- A seropositive subject is a subject whose titre is greater than or equal to the cut-off value.
- The GMTs calculations are performed by taking the anti-log of the mean of the log concentration/titre transformations. Values to be used for the antibody concentrations/titres below the assay cut-off will be described in the Statistical Analysis Plan (SAP).
- Handling of missing data: for a given subject and a given immunogenicity measurement, missing or non-evaluable measurements will be replaced only if values before and after are available. In such an occurrence, the following rule will apply:
  - The missing value will be imputed to be equal to the lowest one between the previous and the subsequent available values (conservative approach).
  - Subjects receiving a booster dose because their NT <10 will be kept in the analysis of persistence until year 15 with an NT imputed value equal to 1.

In case of significant non-compliance of study procedures for reporting symptoms, the analysis plan will be reassessed to ensure more accurate reporting of study data by further analysis.

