### **10.7.2. Statistical Methods for Immunogenicity Variables**

Long-term immunogenicity (persistence).

- Percentages of subjects with neutralizing antibody titres  $\geq 2$  and  $\geq 10$  as measured by NT assay will be tabulated by vaccine schedule (as assigned from the parent study) together with the associated two-sided 95% Clopper-Pearson confidence intervals (CIs). The vaccine group difference in the percentage of subjects with neutralizing antibody titres  $\geq 2$  and  $\geq 10$  will be calculated using a binomial distribution. The associated confidence interval for these differences will be constructed using the Miettinen-Nurminen method.
- GMTs with the associated 95% CIs will be computed for each vaccine schedule (as assigned from the parent study), by taking the exponential of the corresponding log10-transformed (least squares) means and 95% confidence intervals, from an ANOVA model with group as fixed factor. Vaccine schedule differences along with 95% CIs will also be computed.

Subjects with antibody levels below 10 at a given visit (and that will therefore receive a booster dose) will be kept in the analysis of persistence also for the subsequent years with a value imputed to half of the detection limit, i.e. 1.

Analyses will be conducted on the PPS-1 (and repeated on the FAS-1, if appropriate).

Immune response to booster dose (boostability):

- Percentages of subjects with neutralizing antibody titres  $\geq 2$  and  $\geq 10$  at 21 days after administration of the booster dose, as measured by NT will be tabulated by vaccine schedule (as assigned from the parent study) together with the associated two-sided 95% Clopper-Pearson CIs.

- GMTs with the associated 95% CIs at 21 days after administration of the booster dose, will be computed for each vaccine schedule (as assigned from the parent study), by taking the exponential of the corresponding log10-transformed (least squares) means and 95% confidence intervals, from an ANOVA model with group as fixed factor.
- GMRs with the associated 95% CIs after/before booster as measured by GSK Biologicals' NT calculated for each of the different schedule groups.

Computationally, the antibody value as recorded 6 months prior to the booster visit (i.e. at the previous scheduled clinic visit) will be considered as baseline.

All analyses will be repeated for each age subgroup.

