6.3. Immunogenicity**6.3.1. Analysis of immunogenicity planned in the protocol**

The primary analysis population for immunogenicity is the per protocol set and if, in any study group, the percentage of subjects with serological results excluded from the PP set is at least 10%, a second analysis will be performed on the FAS. All analyses entail the calculation of summary statistics by vaccination schedule and age stratification, together with their 95% confidence intervals.

Long-term immunogenicity (persistence).

- Percentages of subjects with neutralizing antibody titres ≥ 2 and ≥ 10 as measured by NT assay will be tabulated by vaccine schedule (as assigned from the parent study) together with the associated two-sided 95% Clopper-Pearson confidence intervals (CIs). The vaccine schedule difference in the percentage of subjects with neutralizing antibody titres ≥ 2 and ≥ 10 will be calculated using a binomial distribution. The associated confidence interval for these differences will be constructed using the Miettinen-Nurminen method.
- GMTs with the associated 95% CIs will be computed for each vaccine schedule (as assigned from the parent study), by taking the exponential of the corresponding log10-transformed (least squares) means and 95% confidence intervals, from an ANOVA model with group as fixed factor. Vaccine schedule differences along with 95% CIs will also be computed.

SAS code

The SAS statements to calculate the adjusted GMCs will be similar to:

```
PROC glm;  
  BY vaccinegroup;  
  CLASS group;  
  MODEL log_Ab=group;  
  LSMEANS group / tdiff stderr;  
RUN;
```

Between-group ratios of GMTs will be calculated by including additional SAS statements within PROC GLM, similar to:

```
ESTIMATE 'Group 1 - Group 2' group 1 -1;
```

Subjects with antibody levels below 10 at a given visit (and that will therefore receive a booster dose) will be kept in the analysis of persistence also for the subsequent years with a value imputed to half of the detection limit, i.e. 1.

Analyses will be conducted on the PPS-1 (and repeated on the FAS-1, if appropriate).

Immune response to booster dose (boostability):

- Percentages of subjects with neutralizing antibody titres ≥ 2 and ≥ 10 at 21 days after administration of the booster dose, as measured by NT will be tabulated by vaccine schedule (as assigned from the parent study) together with the associated two-sided 95% Clopper-Pearson CIs.

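### A subject already read below NT 10 can be withdrawn unboosted at the booster visit, and the plan does not say consistently how that subject then counts for persistence

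*Protocol*

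**What the plan says.** **Who attends the booster visit.** The footnote to Protocol Table 11 reads in part: "Only subjects with an NT antibody titre below 10 at a scheduled visit will receive 6 months later at an unscheduled visit a second booster". Table 6 says the same.

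**What happens if the subject is ill.** For a temporary contraindication, Protocol 6.5 says that such a subject "may be vaccinated at a later date, within the time window specified in the protocol, or withdrawn at the discretion of the investigator". For an absolute contraindication, the same section says that "the subject must not receive a dose of vaccine but may continue other study procedures at the discretion of the investigator". Section 5.6.12 mentions only rescheduling: if the subject's "health on the day of vaccination temporarily precludes vaccination, the visit will be rescheduled". Sections 5.6.15 and 5.6.17 also reschedule, within the allowed interval. Section 9.2.2, "Subject withdrawal from study vaccine", is marked as not applicable.

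**How a failure counts afterwards.** Three places deal with this.
- Protocol 10.5: "Subjects receiving a booster dose because their NT <10 will be kept in the analysis of persistence until year 15"; the imputed titre is 1. Any other missing value is imputed only if the subject has a value both before and after it.
- Protocol 10.7.2: "Subjects with antibody levels below 10 at a given visit (and that will therefore receive a booster dose) will be kept in the analysis of" (the sentence goes on to cover persistence in later years, again at a titre of 1).
- SAP 6.3.1 repeats the 10.7.2 rule and gives the value as 1, half the detection limit. SAP section 9 lists no change from the protocol.

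**The waning description.** Protocol 10.2 and SAP 4.2 and 6.3.2 limit it to subjects who complete the 15-year follow-up without protocol deviations. Boosted subjects stay in it at NT = 1.

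**The concern.** The withdrawal option depends on the primary outcome. A subject who stays at NT ≥10 is never called to a booster visit and never meets it. Because withdrawal from vaccine alone is set aside in 9.2.2, the natural meaning of withdrawn in 6.5 is leaving the study. The temporary condition therefore carries a harsher consequence for follow-up than the absolute one.

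The yearly percentage at NT ≥10 and the GMT are the primary results, and the protocol intends them to guide the timing of the second booster. If known failures leave the denominator while successes stay, both figures rise for a reason unrelated to antibody persistence. Under 10.5, FAS-1 and PP-1 lose the same later values, so comparing the two sets would not show the effect.

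**Working it through.** **1. Follow one subject through the rules.** Take a subject read below 10 at Year 11, ill at Visit 23.1 and withdrawn without a booster.

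| Analysis | Protocol 10.5 (trigger: booster given) | Protocol 10.7.2 and SAP 6.3.1 (read as trigger: titre below 10) |
|---|---|---|
| Year 11 summaries | Counted as observed; 9.2.1 uses data up to withdrawal | Same |
| Year 12 to 15 summaries | No NT = 1, since no booster; no other imputation, since no later value. Absent | NT = 1 each year. Counted as a failure |
| NT-waning description | Not a completer (9.1, 9.2.1), so absent | Same: absent |

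The two readings give different yearly results. Neither keeps the subject in the waning description, although a boosted failure remains there.

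**2. Inputs.** Protocol Table 1 gives C 51, R 46 and AC 103; 51 + 46 + 103 = 200, which agrees with the stated total. Section 4.1 says that the number falling below 10 cannot be estimated, and no withdrawal rate is given. The failure rate is therefore my assumption: about 10%, with a range of 5% to 20%. The only anchor is the statement in 1.2 that above 90% were at NT ≥10 for at least 10 years. It is a loose one, because 4.3 excludes anyone with NT below 10 in V48P7E2.

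**3. Percentage at NT ≥10.** With N subjects, F failures and w failures withdrawn unboosted:
- kept as NT = 1: (N − F)/N
- dropped: (N − F)/(N − w)

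| Group | N | F | Kept | w = 1 | w = 2 |
|---|---|---|---|---|---|
| C | 51 | 5 | 46/51 = 90.2% | 46/50 = 92.0% (+1.8) | 46/49 = 93.9% (+3.7) |
| R | 46 | 5 | 41/46 = 89.1% | 41/45 = 91.1% (+2.0) | 41/44 = 93.2% (+4.1) |
| AC | 103 | 10 | 93/103 = 90.3% | 93/102 = 91.2% (+0.9) | 93/101 = 92.1% (+1.8) |
| All | 200 | 20 | 180/200 = 90.0% | 180/199 = 90.5% (+0.5) | 180/198 = 90.9% (+0.9) |

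Over assumed persistence of 80% to 95%, one dropped failure adds 0.4 to 0.5 points overall, 1.6 to 1.9 in C, 1.8 to 2.1 in R and 0.8 to 0.9 in AC. The direction is always upward. For scale, the Clopper-Pearson 95% interval for 46/51 is 78.6% to 96.7%, and for 46/50 it is 80.8% to 97.8%.

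**4. GMT.** Assume that the non-failures have geometric mean G and that each failure counts as 1. Since log10(1) = 0, log10 GMT is (N − F) × log10(G)/N if all are kept and (N − F) × log10(G)/(N − w) if w are dropped. With G = 100 and w = 1, R moves from 60.6 to 66.4 (ratio 1.10) and the whole cohort from 63.1 to 64.4 (ratio 1.02). For G from 50 to 200, the ratio runs from 1.08 to 1.11 in R and is about 1.02 overall.

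**5. Titre-triggered reading.** The withdrawn failure stays in the denominator as a failure, so the change in the percentage at NT ≥10 is 0.

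**The case against.** The strongest objection is that the plan already has a rule for failures. Protocol 10.7.2 and SAP 6.3.1 name the titre, not the booster, when they say who is kept at NT = 1. A reader might infer from 6.5 that the persistence percentage is simply biased upward over Years 12 to 15. The documents do not support that:
- On the titre reading, the percentage at NT ≥10 is unaffected.
- The visit with the failing titre still counts, and the subject remains in FAS-1, which needs only one evaluable sample. Only later visits are lost.
- Only a Year 11 failure could lose all four later years. A subject who fails at Year 15 has already given that titre.
- SAP 6.3.2 allows a repeated-measures model that would use the failing titre, although it is optional and covers the GMT only.

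The conflict over rescheduling can also be overstated. Rescheduling within the window is the first option in 6.5, and 5.6.15 and 5.6.17 do not address a missed window. A reader might infer that illness late in the window forces withdrawal. However, 5.7.5 sends subjects with an exclusion against study vaccination to care outside the study without mentioning withdrawal, and the note to Table 6 names only possible per-protocol elimination for visits out of range.

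Finally, this route needs moderate or severe illness and no later vaccination, so the numbers are probably small. That is a judgement; the documents give no figure.

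These points remove the unconditional claim of bias, but not the gap. Both 10.7.2 and SAP 6.3.1 presume in parentheses that the subject will be boosted, 10.5 requires it, and the waning description loses the subject on either reading.

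**Conclusion.** The point holds in conditional form. Section 6.5 opens an exit that only known failures can take, and the plan does not settle how they then count. A failure withdrawn unboosted before Year 15 is lost from the waning description on any reading. The later yearly percentages and GMTs can be biased upward if 10.5 governs; the percentage at NT ≥10 is not biased if the titre reading of 10.7.2 and SAP 6.3.1 governs.

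The total size cannot be stated. The per-subject effects above rest on the assumed failure rate and, for the GMT, on an assumed G. They are small for the whole cohort and more visible in C and R, where one or two subjects move the estimate by about 2 to 4 points. Even there, the shift is well inside the confidence interval. The change is worth making because the direction is known and the correction is cheap.

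**What to change.** 1. **Participation.** Reconcile Protocol 6.5 with 5.6.12, 5.6.15, 5.6.17 and 9.2.2 on whether a subject who is not boosted may remain in the yearly blood draws, and on what withdrawn means in 6.5. Vaccination and medical decisions stay with the investigator.
2. **Analysis rule.** Use one sentence in Protocol 10.5, Protocol 10.7.2 and SAP 6.3.1: from the first NT below 10, a subject counts as NT = 1 at all later scheduled visits, whatever the booster or withdrawal status. Keep such subjects in the set for the waning description (Protocol 10.2, SAP 4.2 and 6.3.2).
3. **Reporting.** Give the number with NT below 10 who were not boosted, by schedule group. Add a sensitivity analysis that uses any later titres observed in these subjects in place of 1, because the rule in item 2 would otherwise overwrite real data.

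The cost is a few sentences, one row in the disposition table and one extra analysis. If unboosted subjects do remain in follow-up, there are a few additional annual samples, at most four for a Year 11 failure. The persistence figures may come out slightly less favourable than under 10.5 as written.

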## **6.6. Warnings and precautions**

Refer to the approved product label/package insert.

## **6.7. Concomitant medications/products and concomitant vaccinations**

At each study visit, the investigator or delegate should question the subject about any medications/products taken and vaccinations received by the subject.

### **6.7.1. Recording of concomitant medications/products and concomitant vaccinations**

The following concomitant medication(s)/product(s)/vaccine(s) must be recorded in the eCRF.

For all subjects:

- Relevant medications/products:
  - Systemic administration of corticosteroids (PO/IV/IM) for more than 14 consecutive days within 90 days prior to all blood draws. This will mean prednisone  $\geq$  20 mg/day (for adult subjects), or equivalent. Inhaled and topical steroids are allowed.
  - Administration of antineoplastic and immuno-modulating agents or radiotherapy within 90 days prior to all blood draws.
  - Received immunoglobulins or any blood products within 180 days prior to blood draw.
  - Administration of long-acting immune-modifying drugs administered at any time during the study period (e.g. infliximab).
  - Information on the vaccinations administered since the completion of the V48P7E2 study and prior to enrolment into this study.
- Any concomitant medications/products/vaccines relevant to a SAE to be reported as per protocol or administered during the study period for the treatment of a SAE. In addition, concomitant medications relevant to SAEs need to be recorded on the expedited Adverse Event report.

For subjects who will need an unscheduled second booster vaccination the following concomitant medications/products/vaccinations should also be recorded:

- All concomitant medications/products, except vitamins and dietary supplements, administered during the period starting 7 days before booster vaccination and up to 28 days after booster vaccination.
- Any concomitant vaccination administered in the period starting 28 days before the booster dose of study vaccine and ending at the last study visit.

- Prophylactic medication (i.e. medication administered in the absence of ANY symptom and in anticipation of a reaction to the vaccination).  
E.g. an anti-pyretic is considered to be prophylactic when it is given in the absence of fever and any other symptom, to prevent fever from occurring [fever is defined as temperature  $\geq 38.0^{\circ}\text{C}/100.4^{\circ}\text{F}$  regardless of the location of measurement]. The preferred location for measuring temperature in this study will be the oral cavity.
- Any concomitant medications/products/vaccines listed in Section 6.7.2.

#### **6.7.2. Concomitant medications/products/vaccines that may lead to the elimination of a subject from per-protocol analyses**

The use of the following concomitant medications/products/vaccines will not require withdrawal of the subject from the study but may determine a subject's evaluability in the per-protocol analysis. See Section 10.4 for analyses sets to be analysed.

##### **For all subjects:**

- Any investigational or non-registered product (drug or vaccine) other than the study vaccine used during the study period.
- Immunosuppressants or other immune-modifying drugs defined as follows:
  - Systemic administration of corticosteroids (PO/IV/IM) for more than 14 consecutive days within 90 days prior to all blood draws. This will mean prednisone  $\geq 20$  mg/day (for adult subjects), or equivalent. Inhaled and topical steroids are allowed.
  - Administration of antineoplastic and immuno-modulating agents or radiotherapy within 90 days prior to all blood draws.
- Received immunoglobulins or any blood products within 180 days prior to blood draw.
- Administration of long-acting immune-modifying drugs administered at any time during the study period (e.g. infliximab).

